10.5 Privacy of Personal Data

The subject's name and personal data will remain confidential and will not be published in any way. All reports and communications relating to study subjects will identify the subject only by his/her subject number and study 3-letter code. The Study staff will complete subject identification in a confidential enrolment log, which will be used for the purposes of traceability and follow-up. This will be treated with strict adherence to professional standards of confidentiality and will be filed under adequate security and restricted accessibility.

11.1 Case Report Forms (CRFs)

Paper case report forms will be used in this trial. All protocol-required information collected during the study must be entered in the appropriate field of the case report form (CRF). The investigator, or designated representative, should complete the appropriate CRF fields as soon as possible after information is collected. The information must match the information that exists as source documents in

| | | |
|---------------------------------------------------------------------------------|-----------------------------------------------------------------|-----------------------|
|  | Treatment with the Evoke System for Facial and Submental Laxity | |
| | Protocol No: DO609886A SIRB ID: | Rev. Date: 29 Oct. 20 |

the clinic chart, hospital chart, and/or investigator's files. An explanation should be given for all missing data.

It is the investigator's responsibility to assure the accurate completion, review, and approval of all CRFs and the timely completion and submission of all adverse event forms.

11.2 Maintenance and Retention of Records

Investigators will maintain all study related documentation for a period of five years following: 1) marketing authorization for device commercialization, or 2) sponsor's withdrawal of submission for approval, or 3) completion of the study, if the investigational device is already approved for commercialization.

All printouts and records of tests and procedures are to be kept in a secure and safe place throughout the study. Once the study is completed, the records will be kept as required by local regulations, but in no case less than the period defined above.

The Investigator will not relocate or dispose of any study documents before obtaining sponsor's written permission.

Documentation should be kept so as to make its retrieval easy should an audit take place.

All study documentation will be kept locked under the Investigator's responsibility.

11.3 Reports

Study reports include a Final Report that will be issued by the Sponsor. Report format will be designed by the Sponsor.

All study reports will be signed by the Principal Investigators approving its contents, analysis, results and conclusions.

AE related reporting requirements are specified above.

12. Monitoring Plan

12.1 General Considerations

Monitoring functions will be performed in compliance with Good Clinical Practices, EN ISO 14155, and as outlined in 21CFR§812.43(d) and 21CFR§812.46. InMode Ltd procedures detail monitoring procedures and monitor responsibilities.

The study will be monitored by the sponsor periodically at the site, per Sponsor discretion.

| | | |
|---------------------------------------------------------------------------------|-----------------------------------------------------------------|-----------------------|
|  | Treatment with the Evoke System for Facial and Submental Laxity | |
| | Protocol No: DO609886A SIRB ID: | Rev. Date: 29 Oct. 20 |

12.2 On-Site Visits

Periodic on-site monitoring visits are intended to assess the Investigator's adherence to the protocol, maintenance of records and reports, and review of source documents for accuracy, completeness, and legibility, and monitoring of Adverse Events.

During periodic visits the monitor is required to:

- Assess the progress of the study towards meeting study objectives.
- Identify any concerns that stem from observations of device performance and/or review of the subject's CRF, study management documents, and informed Consent documents.
- Monitor AE reporting and investigations.

Reports of on-site visits will be submitted by the monitor and will include, as applicable, resolution of concerns, completion of appropriate follow-up activities, completion of assigned tasks, and corrective actions. Some 'visits' may be performed using a conference call/video conference call and will not be actual physical visits.

12.3 Site Initiation Meeting

A Site Initiation visit will take place prior to initiation of study procedures. All study related documents and procedures will be explained to all staff involved in the study to ensure understanding of the study requirements. Suitability of potential study subjects will also be evaluated prior to their inclusion.

12.4 Adverse Event Reporting and Follow-up

Monitoring of adverse events, their follow up and outcomes will take place at each study visit.

12.5 Site Closure Visit

A Site Closure Visit will be conducted to ensure that all relevant documentation is filed and archived under the Investigator's responsibility according to regulations.

13. Risk/Benefit Analysis

13.1 Expected Risks:

As indicated in section 10.2 possible Evoke handpiece adverse effects include but are not limited by:

- discomfort or pain,
- excessive skin redness (erythema)
- swelling (edema),
- damage to natural skin texture (crust, blister and burn),
- change of pigmentation (hyper- and hypo-pigmentation),
- bruising,
- scarring.

| | | |
|---------------------------------------------------------------------------------|-----------------------------------------------------------------|-----------------------|
|  | Treatment with the Evoke System for Facial and Submental Laxity | |
| | Protocol No: DO609886A SIRB ID: | Rev. Date: 29 Oct. 20 |

These risks are minimal when compared to other methods of skin tightening that are being utilized (such as surgical facelift).

13.2 Expected Benefits:

The expected benefit of using the Evoke is achieving the desired skin improvement via non invasive technique. It is obvious that the low risk profile of the RF utilizing Evoke device greatly benefits the individual seeking treatment for skin appearance improvement and wrinkles reduction as it significantly minimizes the risks associated with other techniques such as surgery.

13.3 Conclusion:

It can therefore be claimed that the expected benefits associated with the use of the Evoke device outweigh its risks.

14. Data analysis

14.1 Analysis Sets

- Safety Analysis Set

The safety analysis set will include all subjects using Embrace procedures at least a single time.

- Performance Analysis Set

Performance analysis set will consist of all subjects providing at least one post treatment performance measurement.

- Treatment of Missing Values

Only observed data will be used; i.e. missing data will not be imputed.

14.2 Statistical Analysis

Means, and standard deviations for each characteristic will be calculated. Paired sample t-test will be computed to assess changes in before treatment and follow-up scores. Statistical significance will be calculated and two-tail significance level of 0.05 will be used.

15. Data Management Plan

Case Report Forms will be retrieved by Monitors after verification and resolution of monitoring queries. Documents will be delivered to InMode Ltd onsite data management facility where forms will be logged in, and then data will be entered into a prepared Excel file.

Data will be entered using a double entry method and controlled by periodic and random validation check.

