| Efficacy Endpoints | 
 1. Improvement in skin appearance comparing pre and at 1 month (except site #3), 3 months and 6 months post last treatment photographs (as assessed by blinded investigators): 
 • Success is defined by correct identification of the pre and post treatment photos of patients completed the treatment at 1 month (except site #3), 3 months and 6 months post treatment. • At least 2 out of 3 blinded evaluators should agree on the assessment. 2. 3D Photographic analysis will be conducted at 1 month (except site #3), 3 months and 6 months follow up visits and compared to the baseline. 3. Investigator assessment of the skin appearance improvement comparing pre and post treatment using 0 - 4 -points Likert scale at 1 month (except site #3), 3 months and 6 months follow up visits: 
 • 4 = Significantly marked improvement; 3 = Marked improvement; 2 = Moderate improvement; 1 = Slight improvement; 0 = No difference 4. Improvement assessment will be performed independently by the subject himself 4 points Likert scale questionnaire (Global Aesthetic Improvement Scale), as follows: 
 • 4 = Significantly marked improvement; 3 = Marked improvement; 2 = Moderate improvement; 1 = Slight improvement; 0 = No difference. 5. Subject assessment of satisfaction will be filled out by subjects using a 5-points Likert scale, as follows: 
 • +2 = Very satisfied; +1 = Satisfied; 0 = Indifferent; -1 = Disappointed; -2 = Very disappointed. 6. Optional: Positive changes in histologic evaluation: up to 5 subjects will undergo biopsies of the treated area for histology at baseline and at 3M follow-up visit. Histological sections will be stained using elastin, H&E and other collagen specific stains. (except site #3) |

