The aim of the study is to evaluate the efficacy, patient comfort and patient satisfaction after Evoke treatment.

Primary Objective:

1. Evaluate improvement in skin appearance comparing pre and at 1 month (except site #3), 3 months and 6 months post last treatment photographs (as assessed by blinded investigators)
2. Evaluate Improvement in skin appearance using 3D Photographic analysis at 1 month (except site #3), 3 months and 6 months follow up visits and compared to the baseline.

Secondary Objective:

1. Evaluate Investigator assessment of the skin appearance improvement comparing pre and post treatment using 0 - 4 -points Likert scale at 1 month (except site #3), 3 months and 6 months follow up visits.

| | | |
|--------------------------------------------------------------------------------------------------------|------------------------------------------------------------------------|-----------------------|
|  I N M O D E | Treatment with the Evoke System for Facial and Submental Laxity | |
| | Protocol No: DO609886A SIRB ID: | Rev. Date: 29 Oct. 20 |

2. Evaluate Subject assessment of improvement and satisfaction using 0 - 4 -points Likert scale at 1 month (except site #3), 3 months and 6 months follow up visits.
3. Optional: Evaluate histological changes to treatment area skin taken at 3M FU versus baseline. (except site #3)

6. Study Endpoints

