6.1 Efficacy Endpoints

1. Improvement in in skin laxity comparing pre and at 1 month (except site #3), 3 months and 6 months post last treatment photographs (as assessed by blinded investigators):
 - Success is defined by correct identification of the pre and post treatment photos of patients completed the treatment at 1 month (except site #3), 3 months and 6 months post treatment.
 - At least 2 out of 3 blinded evaluators should agree on the assessment.
2. 3D Photographic analysis will be conducted at 1 month (except site #3), 3 months and 6 months follow up visits and compared to the baseline.
3. Investigator assessment of the skin appearance improvement comparing pre and post treatment using 0 - 4 -points Likert scale at 3 months and 6 months follow up visits:
 - 4 = Significantly marked improvement; 3 = Marked improvement; 2 = Moderate improvement; 1 = Slight improvement; 0 = No difference
4. Improvement assessment will be performed independently by the subject himself 4 points Likert scale questionnaire (Global Aesthetic Improvement Scale), as follows:
 - 4 = Significantly marked improvement; 3 = Marked improvement; 2 = Moderate improvement; 1 = Slight improvement; 0 = No difference.
5. Subject assessment of satisfaction will be filled out by subjects using a 5-points Likert scale, as follows:
 - +2 = Very satisfied; +1 = Satisfied; 0 = Indifferent; -1 = Disappointed; -2 = Very disappointed.
6. Optional: Positive changes in histologic evaluation: up to 5 subjects will undergo biopsies of the treated area for histology at baseline and at 3M follow-up visit. Histological sections will be stained using elastin, H&E and other collagen specific stains.

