7.2 Subject Withdrawal and Replacement

Subjects enrolled in the study can discontinue their participation at any time for any reason without prejudice or reduction in the quality of their medical care. The investigators or sponsor can terminate a subject's participation in this study to protect the subject's health or if the subject fails to follow directions resulting in noncompliance to study procedures. Subjects who withdraw or are terminated from the study may be replaced to ensure approximately 15 subjects (per site) have completed the study. Subjects who fail to complete the treatment will be replaced and will not be evaluable.

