8.3 Follow up visits (Visits 4, 5 and 6)

Follow up visits will be conducted at 4 weeks (1-month FU) (except site #3), 12 weeks (3M FU) and 24 weeks (6M FU) following last treatment.

The 1 month (except site #3), **3 months and 6 months follow up visits** will include the following assessments:

- Standardized medical photography
- 3D Photography

| | | |
|--------------------------------------------------------------------------------------------------------|------------------------------------------------------------------------|-----------------------|
|  I N M O D E | Treatment with the Evoke System for Facial and Submental Laxity | |
| | Protocol No: DO609886A SIRB ID: | Rev. Date: 29 Oct. 20 |

- Urine Pregnancy Test (only last 6 months FU visit)
- Investigator assessment of the skin appearance improvement comparing pre and post treatment using 4-point Likert scale
- Subject’s Improvement and Satisfaction questionnaires
- Post final treatment biopsy will be performed (up to 5 subjects)
- AE evaluation recording
- Concomitant medication recording

9. Adverse Events Reporting

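### The blinded photo-identification endpoint for Primary Objective 1 has no planned test and no chance or target rate; the paired t-test in Section 14.2 cannot be applied to it

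*Combined protocol and SAP*

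**What the plan says.** The first primary objective (Synopsis and Section 5) reads: "Evaluate improvement in skin appearance comparing pre and at 1 month (except site #3), 3 months and 6 months post last treatment photographs", as judged by blinded investigators. The matching endpoint is item 1 of Section 6.1: "Success is defined by correct identification of the pre and post treatment photos of patients completed the treatment", followed by the rule "At least 2 out of 3 blinded evaluators should agree on the assessment". The Synopsis has the same definition.

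The analysis is in Section 14.2. It offers a summary, "Means, and standard deviations for each characteristic will be calculated", and one test, "Paired sample t-test will be computed to assess changes in before treatment and follow-up scores", at a two-sided 0.05 level.

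On the denominator, Section 6.1 refers to patients who completed treatment, and Section 7.2 agrees: "Subjects who fail to complete the treatment will be replaced and will not be evaluable". Section 14.1 instead defines the performance set as anyone with at least one post-treatment measurement. Section 8.3 schedules follow-up at 1, 3 and 6 months, with no 1-month visit at site #3.

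**The concern.** A paired t-test compares two scores from the same subject. Photo identification yields one binary result per subject and visit, and that result already uses both photographs, so there is no before-treatment score to pair it with. The mean of the binary results is the success proportion, but nothing in Section 14.2 says what to compare it with.

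The proportion cannot be interpreted without a reference value, because evaluators who see no difference will still be right some of the time. How often depends on two things the supplied text leaves open: whether an evaluator must choose or may answer 'cannot tell', and whether success is counted at each visit or only when every visit is correct. No control arm is described that could supply a comparison. If the plan is followed as written, a success rate will be reported for a primary objective and the reader will be unable to tell it from guessing.

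**Working it through.** The documents give no chance rate, target rate, power or sample-size calculation, so there is no stated figure to reproduce. The following shows what the missing reference value would imply.

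**Inputs from the documents.** About 15 subjects per site and five listed sites (Synopsis): 5 × 15 = 75 subjects, or 4 × 15 = 60 at 1 month without site #3. Three evaluators with a 2-of-3 rule (Section 6.1). Two-sided 0.05 (Section 14.2).

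**Assumptions not in the documents.** Forced choice between two photographs in random order; success counted per visit; at least two evaluators correct; all 15 subjects per site evaluable.

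**Chance rate.** If each evaluator is correct with probability p, independently, the majority is correct with probability 3p²(1 − p) + p³. At p = 0.5 this is 0.375 + 0.125 = 0.50. The 2-of-3 rule does not lower the chance rate.

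**Counts needed to exceed 50%** (exact binomial, two-sided 0.05; Clopper-Pearson interval):

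| Correct | Rate | p | 95% CI | Exceeds chance? |
|---|---|---|---|---|
| 45/75 | 60.0% | 0.105 | 48.0% to 71.1% | no |
| 46/75 | 61.3% | 0.064 | | no |
| 47/75 | 62.7% | 0.037 | 50.7% to 73.6% | yes |
| 36/60 | 60.0% | 0.155 | 46.5% to 72.4% | no |
| 38/60 | 63.3% | 0.052 | | no |
| 39/60 | 65.0% | 0.027 | 51.6% to 76.9% | yes |

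With some loss of evaluable subjects the bar is 44/70 (62.9%, p = 0.041) or 41/65 (63.1%, p = 0.046).

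**Power of that test.** With n = 75 (47 or more correct) it is 0.932 at a true rate of 70% and 0.710 at 65%. With n = 60 (39 or more correct) it is 0.838 and 0.559.

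**Forcing the data through the planned test.** Suppose success were coded 0/1 and compared with an invented baseline of 0. The t-test would then declare pure guessing significant with probability 0.982 at n = 15 and practically 1 at n = 60 or 75.

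**Range under other readings.**
- If a 'cannot tell' answer lowers p to 0.4 or 1/3, the formula gives 0.352 or 0.259 for independent evaluators. If the evaluators always answered alike, the rates would be 0.40 and 0.33.
- If success requires every scheduled visit to be correct and guesses are independent across visits, the chance rate is 0.5³ = 0.125 at four sites and 0.5² = 0.25 at site #3. Pooled, it is (60 × 0.125 + 15 × 0.25)/75 = 11.25/75 = 0.15. The upper-tail probability is 0.0255 at 18 successes and 0.0126 at 19, so the bar is 19/75 (25%). Correlated guesses would move the 15% towards 50%.

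A reported 30/75 (40%) would thus be clearly above chance on the every-visit reading. On the per-visit reading it falls short of 50% and is compatible with guessing (p = 0.105, 95% CI 29% to 52%).

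**The case against.** The strongest reply is that this is an open-label study that sets out to evaluate, with no stated hypothesis, power or study-level threshold. A success proportion is a legitimate descriptive result, and the mean in Section 14.2 delivers it. The second primary objective, 3D photographic analysis against baseline, may suit the paired t-test. This bears on how serious the gap is but does not close it. Section 14.2 commits the study to significance testing, the first primary objective is the one left without a usable test, and a test of 3D measurements says nothing about blinded identification.

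The answer format may be set out in evaluator instructions or appendices that were not available. That is possible, and it is why the chance rate is shown as a range. The contents list places the data analysis in Sections 14.1 and 14.2, both available, and the missing test does not depend on the answer format.

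Some points stand. The every-visit reading is the less natural one, since Section 6.1 lists the visits as time points. Section 6.1 asks evaluators to agree, not to be correct. In a two-way choice at least two of three always agree, so counting two correct is an interpretation that must be written down. A lower limit above 50% shows only that the photographs can be told apart better than by guessing; it sets no target for a worthwhile effect. None of this alters the conclusion.

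**Conclusion.** The concern holds and should be fixed before analysis. The endpoint for Primary Objective 1 has no applicable test and no reference rate, so the plan cannot separate real identification from guessing. Under a forced choice, per-visit counting and 15 evaluable subjects per site, results between 50% and about 62% (up to 46/75) at 3 or 6 months are compatible with guessing but could be presented as positive. At 1 month the same applies up to 38/60. The exact thresholds rest on those assumptions; the mismatch between endpoint and test does not. The planned numbers can support a proper test if the true rate is about 70%, less securely if it is 65%.

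**What to change.** **Section 6.1.** Keep correct identification as the endpoint. State that each pair is shown in random order as a forced choice of which photograph is pre and which is post. Count success per subject and visit when at least two of the three evaluators are correct. State the denominator, for example treatment completers with a photograph pair at that visit, and reconcile it with Section 14.1.

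**Section 14.2.** Report the success proportion at each visit with an exact 95% CI, and test it against 50% with a two-sided exact binomial test. Claim efficacy on this measure only if the lower limit exceeds 50%. If the sponsor wants a higher target, state it in advance. Limit the paired t-test to measures that have a before-treatment score.

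**Deciding visit.** This is separable but best settled in the same edit. Name one visit attended by all sites (3 or 6 months) as deciding and treat the others as supportive. The chance of a false success is 0.0185 at one visit with n = 75. If any of three independent visits may count, it is 1 − (1 − 0.0185)² × (1 − 0.0137) = 0.050; correlation between visits lowers this.

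**Cost.** Wording in two sections and in the evaluator instructions, made as an amendment with IRB approval (Section 10.3). No extra patients, evaluators or visits. The sponsor gives up the option of presenting rates between 50% and about 62% as positive.

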- The treatment attendant should not leave the room after starting the treatment as it is important for the clinician to ensure that all Applicators reach the desired cut-off temperature and that the RF energy is maintained at the cut-off level. This should take approximately 2-5 minutes.
- During the procedure check Applicators position occasionally, as they can be shifted from the original placement.
- After the face is treated with Cheek Applicator (for approximately 45 min), if subject's anatomy allows the under-chin area will be treated with Chin Applicator for another 30-45 minutes using the same technique as with the Cheek Applicator.
- Typical response to treatment is erythema, slight edema.
- Subject will be asked to rate discomfort during the procedure. Discomfort will be assessed based on the Numerical Scale Response (NSR). The subject will be presented a scale with both words and numbers along a horizontal line and asked to make a mark along the scale. The subject will be asked to rate discomfort separately for cheeks and chin areas from 0 to 10, with 0 equalling no discomfort and 10 equalling the worst possible discomfort. A number is obtained by measuring up to the point the subject has indicated.
- After each treatment, observation, assessment and recording of adverse events will be conducted.

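### Two primary measures at up to three visits, with no named primary comparison or success rule, and no applicable test for photo identification

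*Combined protocol and SAP*

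**What the plan says.** Section 5 (Study Objectives), like the synopsis, lists two items under the primary objective and ranks neither first:

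- Photographs read by blinded investigators: "Evaluate improvement in skin appearance comparing pre and at 1 month (except site #3), 3 months and 6 months post last treatment photographs".
- 3D imaging: "Evaluate Improvement in skin appearance using 3D Photographic analysis at 1 month (except site #3), 3 months and 6 months follow up visits", compared with baseline.

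Section 6.1 defines the photo outcome: "Success is defined by correct identification of the pre and post treatment photos of patients completed the treatment". It adds: "At least 2 out of 3 blinded evaluators should agree on the assessment". It names no variable for the 3D analysis.

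Section 14.2 gives means and standard deviations, then one test: "Paired sample t-test will be computed to assess changes in before treatment and follow-up scores". The level follows: "Statistical significance will be calculated and two-tail significance level of 0.05 will be used".

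On treatment area, Section 8.2 says that if the subject's "anatomy allows the under-chin area will be treated with Chin Applicator", so some subjects may have the cheeks treated only. Subjects "rate discomfort separately for cheeks and chin areas", but nothing comparable is said for the photo or 3D outcome.

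**The concern.** A significance level has a clear meaning only when the reader knows which test it governs. Here up to six results sit under one primary objective (two measures at three visits; four at site #3), and nothing says which of them answers it. The choice could be made after the results are known.

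The second problem does not depend on multiplicity. A paired t-test needs a before value and an after value for each subject. Photo identification yields one correct or incorrect result per photo pair, so there is no difference to test. The 2-of-3 rule concerns a single assessment. It does not say what share of subjects must be correctly identified, or against what rate that share is judged.

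**Working it through.** **Inputs.** Two-sided 0.05 and a paired t-test (Section 14.2). Two measures, three visits, no 1-month visit at site #3 (Section 5). Five sites listed and about 15 subjects per site (synopsis). The plan gives no power, effect size, standard deviation, target rate or between-visit correlation, so it has no calculation to reproduce. The 0.05 is a stated choice and is the error rate of one test.

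**Step 1: which results the named test can serve.**
- 3D analysis: if it yields a numeric score at baseline and follow-up, the paired t-test fits. That gives at least three tests, one per visit; more if several 3D variables or areas are scored.
- Photo identification: no before score, so the test does not apply.

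**Step 2: false improvement across the three 3D tests, if any one is enough.** A two-sided 0.05 test has a 0.025 chance of a false result in the direction of improvement.
- Independent: 1 − 0.975³ = 0.073.
- Equally correlated normal tests, by simulation (2,000,000 draws): 0.063 at correlation 0.5; 0.049 at 0.8.
- Paired t-tests on simulated subjects, with n = 60, 75 and 75 at 1, 3 and 6 months: 0.073, 0.064 and 0.053 at correlations 0, 0.5 and 0.8.

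The changes share one baseline. With equal variances σ² and equal between-visit correlation ρ, each change has variance 2σ²(1 − ρ) and any two have covariance σ²(1 − ρ). Their correlation is therefore 0.5, which makes the middle figure, about 6%, a reasonable centre.

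**Step 3: the same tests, if all must succeed.** Falsely winning on all three cannot be more likely than falsely winning on one, so the chance is at most 0.025. At correlation 0.8 it is 0.007.

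**Step 4: reference rate for the photos.** If three readers guess independently at 50%, the chance that at least two are correct is 3(1/8) + 1/8 = 0.50. About half of subjects would then count as successes with no visible change, so a bare success share cannot be interpreted without that reference.

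**Step 5: what a suitable test would require.** Exact binomial test against 50%, two-sided 0.05 (upper tail at most 0.025):

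| Evaluable subjects (assumed) | Correct needed | Two-sided p | One fewer correct |
|---|---|---|---|
| 75 (5 × 15) | 47 (62.7%) | 0.037 | 46: p = 0.064 |
| 60 (4 × 15) | 39 (65.0%) | 0.027 | 38: p = 0.052 |

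Power is 93% with 75 subjects if the true rate is 70%, and 71% if it is 65%. With 60 subjects it is 84% and 56%.

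**The case against.** The strongest reply is that this is an open-label study with no comparator, whose stated aim is to evaluate. It makes no confirmatory claim and gives no power calculation, and the inflated error exists only under a rule the documents never state. That stands as far as the error rate goes: what is shown is a missing specification. It does not remove the point, because the plan commits itself to significance testing at 0.05 and leaves open what that testing is meant to decide.

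Three stronger readings are tempting, and the documents do not support them.

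- *The plan applies a t-test to the photos.* Section 14.2 limits the t-test to before and follow-up scores and never assigns it to photo identification. The supportable statement is that no applicable test is named for that outcome.
- *The error rate is about 26%.* Six independent tests give 1 − 0.95⁶ = 0.265, but three of these would be photo tests that the plan does not contain. The figure also counts false worsening, which could not support a claim of improvement.
- *The treatment area is undefined.* The synopsis and Section 8.2 name the face and the area under the chin, and the separate cheek and chin ratings concern discomfort. What remains is narrower: how subjects without chin treatment are scored.

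It may also be said that Section 6.1 already has a success rule. It does, but only for an individual assessment. With a two-way choice, two of three readers always agree, so agreement alone adds nothing unless the rule means two of three correct.

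**Conclusion.** The point holds as a gap in specification that should be closed. No measure, visit, test order or any/all rule is fixed for the primary objective, and its first-listed measure has no applicable test or reference rate. The second part follows from the text without any assumption.

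The size of the multiplicity problem is conditional. With no true effect, three 3D tests and an any-one-is-enough reading, a false improvement has a chance of about 5% to 7%, against 2.5% nominal. The range rests on assumed correlations of 0.8 down to 0. Under an all-must-succeed rule there is no inflation. A reader might infer that the trial's error rate is inflated as designed; the documents do not show that, because they adopt neither rule.

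**What to change.** Amend the synopsis and Sections 5, 6.1 and 14.2 as follows.

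1. Name one primary comparison: one measure at 3 or 6 months, visits that all sites collect, tested at two-sided 0.05.
2. Test the other comparisons now under the primary objective in a stated fixed order, stopping at the first non-significant result. The 1-month results may come last in that order or be descriptive, labelled as coming from the sites other than #3.
3. For photo identification, require each evaluator to choose which photo is post-treatment, with display order randomised. Define subject-level success as at least two of three evaluators correct. Test the proportion of successes with a two-sided exact binomial test against 50%.
4. State the denominator. Section 6.1 refers to subjects who completed treatment, Section 7.2 makes non-completers non-evaluable, and Section 14.1 admits anyone with one post-treatment measurement. These need to be reconciled, since the binomial cut-offs depend on the count.
5. Keep the paired t-test for one 3D measure named before analysis, and state how subjects without chin treatment are scored.

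The cost is an IRB-approved amendment (Section 10.3), a display-order list and reader instructions. Under the fixed order, later tests are formal only if earlier ones succeed.
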